9.3 Overdose

In the event of an overdose the investigator should do the following:

- 1) Contact the BMS Medical Monitor/designee immediately
- 2) Closely monitor the subject for AEs/SAEs and laboratory abnormalities until BMS-986165 can no longer be detected systemically (at least 3 days)
- 3) Document the quantity of the excess dose as well as the duration of the overdosing in the eCRF.

Decisions regarding dose interruptions or modifications will be made by the investigator in consultation with the BMS Medical Monitor/designee based on the clinical evaluation of the subject.

9.4 Safety

Planned time points for all safety assessments are listed in the Schedule of Activities ([Section 2](#)). All urgent safety concerns must be discussed with the Sponsor immediately upon occurrence or awareness to determine if the subject should continue or discontinue treatment.

Safety evaluations that will be performed in addition to AE monitoring are physical examination ([Section 9.4.1](#)), TB screening ([Section 9.4.2](#)), vital signs ([Section 9.4.5](#)), ECGs ([Section 9.4.6](#)), concomitant medication use ([Section 7.7](#)), and laboratory tests ([Section 9.4.3](#)).

9.4.1 Physical Examinations

Schedules for physical examinations are provided in the Schedule of Activities ([Section 2](#)). Complete physical examinations must be performed by someone who is authorized to perform the examinations by training and has been delegated this task by the principal investigator. Key aspects of the examination should evaluate important body systems, including skin, as clinically indicated.

Every effort should be made to ensure the same evaluator will complete the examination for each subject at all visits throughout the study. Documentation of who performed the examination is to be recorded in source notes.

9.4.2 Tuberculosis Screening and Chest X-ray

Screening for active TB and LTBI includes medical history, physical examination, [REDACTED] and CXR. A tuberculin skin test (eg, Mantoux test) may also be performed, at the investigator's discretion, but this does not replace the requirement for [REDACTED]. A CXR at the screening visit is required if not already performed and documented within 6 months of obtaining written informed consent.

In order to be eligible for the study, a subject must not have symptoms or signs of active TB, as judged by the investigator.

[REDACTED] is provided as part of the screening investigation kit. This will be collected and sent to a central laboratory. An [REDACTED] test sent to a local laboratory may be an acceptable alternative, provided that this approach is agreed with the BMS Medical Monitor/designee.

A subject with a “negative” [REDACTED] test may be eligible to participate in the study, provided they do not have any clinical or radiologic (CXR) evidence supporting a diagnosis of active TB or LTBI.

A subject with an “indeterminate” QuantiFERON test or a “borderline” T-Spot test must have a retest before they are eligible to participate in the study. If the second result is again “indeterminate” or “borderline,” the subject will be excluded from the study. If the second result is negative, the subject may be eligible provided there is no clinical or radiologic suspicion of active TB or LTBI.

A subject with a positive [REDACTED] result should be further assessed in order to determine if active TB or LTBI is present.

Subjects who are diagnosed with LTBI during screening may be eligible to be rescreened for this study provided they have completed at least 4 weeks of treatment for LTBI and they comply with treatment for LTBI (both according to local standard of care) during study participation. For these subjects, a medical history, physical examination, and a repeat CXR are required during rescreening, but [REDACTED] should not be repeated.

9.4.3 Clinical Safety Laboratory Assessments

- A central or local laboratory will perform safety laboratory assessments (as indicated in operational documents; except [REDACTED] tests and diagnostic SARS-CoV-2 tests [where applicable], which may be performed in clinic [if that is local standard of care]) and provide reference ranges and laboratory reports. The central laboratory is preferred (over the local laboratory) for safety assessments.
- Investigators must document their review of each laboratory safety report.

- Any laboratory test result that the investigator considers clinically relevant for safety is to be recorded on the appropriate AE page of the eCRF ([Section 9.2.6](#)).
- Results of clinical laboratory tests performed during the screening period must be available prior to randomization.
- The timing of laboratory assessments is indicated in the Schedule of Activities ([Section 2](#)).

The laboratory parameters to be assessed for clinical safety throughout the study are listed in Table 11.

Table 11: Summary of Laboratory Parameters used to Assess Clinical Safety

Hematology	

 • Hemoglobin • MCV • MCH • Hematocrit • WBC (Total leukocyte count) 	
 • Platelet count • RBC count 
CBC Differential (including absolute neutrophil count and absolute lymphocyte count)

Chemistry	
AST ALT GGT Total bilirubin Direct bilirubin ALP LDH Creatinine BUN Uric acid Total protein Albumin Sodium Potassium	Chloride Calcium Phosphorus Magnesium Creatine kinase Creatinine clearance (screening only) with eGFR calculated using the MDRD equation (screening only) TSH (with reflex T3/T4 testing for abnormal TSH results) (screening only) Performed after ≥ 10 hour fast at Day 1 and Week 12 (Day 85): Lipid panel (total cholesterol, high-density lipoprotein cholesterol, low-density lipoprotein cholesterol, and triglycerides) Glucose
Coagulation	
PT INR	Either partial thromboplastin time or aPTT
Urinalysis	
Protein Glucose Blood Leukocyte esterase Specific gravity pH	Microscopic examination of the sediment if blood, protein, or leukocyte esterase are positive on the dipstick Spot urine for protein and creatinine

Table 11: Summary of Laboratory Parameters used to Assess Clinical Safety

Additional Analyses	
■	[REDACTED]
■	[REDACTED]
■	[REDACTED]
■	[REDACTED]
■	[REDACTED]
■	[REDACTED]
■	[REDACTED]
■	[REDACTED]
■	[REDACTED]
■	[REDACTED]
■	[REDACTED]
■	[REDACTED]

Stool Tests

- Stool culture: culture for potentially pathogenic enteric bacteria, including (but not limited to) Salmonella, Shigella, Campylobacter, and EHEC (tested at screening visit and when deemed medically appropriate by the investigator) Testing for additional enteric pathogens including bacteria, protozoa, ova, and parasites may be performed based on the investigator’s clinical judgment.
- Stool for Clostridioides (formerly Clostridium) difficile testing: stool for C. difficile Toxin A and B test (EIA) and GDH antigen test (EIA), with reflex to NAAT (C. difficile PCR) if either positive (screening only, performed at central laboratory, or local laboratory). A direct NAAT test approach may be used if discussed with, and approved by, the BMS Medical Monitor/designee.

ALP = Alkaline phosphatase; ALT = alanine aminotransferase; [REDACTED]
 [REDACTED] aPTT = activated partial thromboplastin time; AST = aspartate
 aminotransferase; BUN = blood urea nitrogen; CBC = complete blood count;
 [REDACTED] eGFR = estimated glomerular filtration rate; EHEC = enterohemorrhagic
 Escherichia coli; EIA = enzyme-linked immunosorbent assay; [REDACTED]
 GDH = glutamate dehydrogenase; GGT = gamma glutamyltransferase; [REDACTED]
 [REDACTED] INR = international normalized ratio; LDH = lactate dehydrogenase; MCH = mean
 corpuscular hemoglobin; MCV = mean corpuscular volume; MDRD = modification of diet in renal disease;
 NAAT = nucleic acid amplification test; PCR = polymerase chain reaction; PT = prothrombin time; RBC = red blood
 cell; [REDACTED]
 [REDACTED] TSH = thyroid-stimulating hormone;
 WBC = white blood cell; [REDACTED]

9.4.4 Imaging Safety Assessment

Not applicable.

9.4.5 Vital Signs

Vital signs will be obtained as indicated in the Schedule of Activities (Section 2) and recorded in the relevant eCRF.

9.4.6 Electrocardiograms

ECGs will be performed as indicated in the Schedule of Activities ([Section 2](#)). ECGs will be read locally. Clinically significant ECG findings will be recorded in the relevant eCRF and should be discussed with the BMS Medical Monitor/designee.

[REDACTED]

[REDACTED]

[REDACTED]

[REDACTED]

[REDACTED]

[REDACTED]

[REDACTED]

- [REDACTED]
- [REDACTED]
- [REDACTED]
- [REDACTED]

[REDACTED]

9.6 Biomarkers

The [REDACTED] effects of BMS-986165 will be explored based on biomarker analyses of [REDACTED] biopsy sample collection are in [Table 13](#) and [Table 14](#), respectively.

Further details of blood, biopsy, and stool collection and processing will be provided to the site in the laboratory manual.

[Redacted]

[Redacted]

[Redacted]

[Redacted]

[Redacted]

[Redacted]

[Redacted]

[Redacted text block]

[Redacted text block]

[Redacted text block]

[Redacted text block]

Table 13: Blood and Stool Sample Collection

Study Day of Sample Collection									
Screening	X		X			X	X	X	X
Double-blind On-treatment									
Day 1		X	X	X	X	X	X		
Week 2 (Day 15)			X			X	X		
Week 4 (Day 29)		X	X	X	X	X	X	X	X
Week 8 (Day 57)						X	X		
Week 12 (Day 85)		X	X	X	X	X	X	X	X
Open-label Extension									
Week 16 (Day 113)			X			X	X		
Week 20 (Day 141)						X	X		
Week 24 (Day 169)			X			X	X		
Week 32 (Day 225)						X	X		
Week 40 (Day 281)						X	X		
Week 52 (Day 365) EOT/ET		X	X			X	X	X	X
Follow-up									
Week 56 (Day 393) F/U						X	X		

EOT = end of treatment; ET = early termination;

F/U = follow-up;

█ [REDACTED]
█ [REDACTED]

Table 14: Colon Biopsy Sample Collection [REDACTED]

Study Day of Sample Collection	[REDACTED]	Biopsies/ Gene Expression	[REDACTED]	Biopsy Noninvolved Area ^b
Screening	[REDACTED]	X	[REDACTED]	X
Double-blind On-treatment				
Week 12 (Day 85)	[REDACTED]	X	[REDACTED]	X
Open-label Extension				
Week 52 (Day 365) EOT/ET	[REDACTED]	X	[REDACTED]	X

EOT = end of treatment; ET = early termination; [REDACTED]

^b Biopsy samples will be collected from noninvolved areas, if available, for gene expression.

9.6.1 Additional Research Collection

This protocol will include residual sample storage for additional research (see [Table 15](#)).

For All sites:

Additional research is required for all study participants, except where prohibited by IRBs/ethics committees, prohibited by local laws or regulations, or academic/institutional requirements. Where one or more of these exceptions occurs, participation in the additional research will not be a condition of overall study participation.

- If the IRB/ethics committees and site agree to the mandatory additional research retention and/or collection, then the study participant must agree to the mandatory additional research as a requirement for inclusion in the study.
- If optional participation is permitted and approved, then the study participants may opt out of the additional research retention and/or collection.

Additional research is intended to expand the research and development capability at Bristol Myers Squibb, and will support as yet undefined research aims that will advance our understanding of disease and options for treatment. This may also include genetic/genomic exploration aimed at exploring disease pathways, progression, and response to treatment etc.

Sample Collection and Storage

All requests for access to samples or data for additional research will be vetted through a diverse committee of the study Sponsor’s senior leaders in Research and Development (or designee) to ensure the research supports appropriate and well-defined scientific research activities.

- Residual blood, stool, biopsies, DNA, and RNA samples from [REDACTED] collections (see [Table 1](#) and [Table 2](#)) will be retained for additional research purposes where local laws/regulations allow.
- Residual blood samples from [REDACTED] will also be retained for additional research purposes where local laws/regulations allow.

Samples kept for future research will be stored at the BMS Biorepository in [REDACTED] USA or an independent, BMS-approved storage vendor.

The manager of these samples will ensure they are properly used throughout their usable life and will destroy the samples at the end of the scheduled storage period, no longer than 15 years after the end of the study or the maximum allowed by applicable law.

Transfers of samples by research Sponsor to third parties will be subject to the recipient’s agreement to establish similar storage procedures.

Samples will be stored in a coded fashion, and no researcher will have access to the key. The key is securely held by the investigator at the clinical site, so there is no direct ability for a researcher to connect a sample to a specific individual.

Further details of sample collection and processing will be provided to the site in the laboratory manual.

Table 15: Residual Sample Retention for Additional Research Schedule

Sample Type	Time points for which residual samples will be retained
[REDACTED]	[REDACTED]
DNA and RNA	All
Blood samples (blood, serum, plasma)	All
Stool samples	All

DNA = deoxyribonucleic acid; [REDACTED] RNA = ribonucleic acid

9.7 Medical Resource Utilization and Health Economics

Medical resource utilization and health economics data associated with medical encounters will be collected in the relevant eCRF by the investigator and study site personnel for all subjects during the treatment period of the study. Protocol-mandated procedures, tests, and encounters are excluded.

The data collected may be used to conduct exploratory economic analyses and may include the number and duration of the following:

- UC-related emergency room visits and hospitalizations
- All-cause emergency room visits and hospitalizations

An example of the data collection form to be used is in [APPENDIX 12](#).

9.8 SARS-CoV-2 Testing

Diagnostic testing for SARS-CoV-2 infection refers to [REDACTED] test for SARS-CoV-2 infection, performed according to local standard of care. [REDACTED] testing is preferred. [REDACTED] testing is not acceptable as a diagnostic test for SARS-CoV-2 infection.

Diagnostic testing for SARS-CoV-2 infection should be performed as close as possible to randomization and must be confirmed as “negative” prior to randomization.

Subjects will be screened for AEs (including signs and symptoms of COVID-19) at each study visit. Subjects will be instructed to contact the investigator at any time if they develop an intercurrent illness, including a diagnosis, or signs and symptoms of COVID-19, which will enable close monitoring and additional screening for the infection between study visits.

The investigator should obtain a diagnostic test for SARS-CoV-2 infection if COVID-19 is clinically suspected. If a subject reports having recent direct contact with someone known to have COVID-19, the subject should undergo diagnostic testing for SARS-CoV-2.

IP should be temporarily interrupted in subjects who present with signs and/or symptoms suggestive of COVID-19 while the subject undergoes diagnostic testing for SARS-CoV-2 infection. This testing should be performed as soon as feasible.

Study subjects with a positive diagnostic test for SARS-CoV-2 must be reported to BMS within 24 hours by entering the AE into the EDC.

IP must be temporarily interrupted in subjects who test positive for SARS-CoV-2 infection. Such subjects should continue to be followed by the investigator. Such subjects must meet all the criteria outlined below prior to restarting IP. The final decision to restart IP must be made in consultation with the BMS Medical Monitor/designee.

Subjects with a positive diagnostic test for SARS-CoV-2 infection during the screening period may be considered eligible for the study once they meet all eligibility criteria related to active infection, and after meeting the criteria outlined below.

Criteria to rescreen or recommence IP after a positive SARS-CoV-2 test:

- At least 10 days (20 days for severe/critical illness) have passed since symptoms first appeared or positive test result, and
- At least 24 hours have passed since last fever without the use of fever-reducing medications, and
- Acute symptoms (eg, cough, shortness of breath) have resolved, and
- In the opinion of the investigator, there are no COVID-19 sequelae that may place the subject at a higher risk from receiving investigational treatment, and
- There are no COVID-19 sequelae that may confound the assessment of safety or efficacy within the study, and
- Negative follow-up molecular or antigen test for SARS-CoV-2 based on institutional, local, or regional guidelines, and

- For rescreening only, symptoms must have completely resolved **4 weeks prior to rescreening**, and based on investigator assessment in consultation with the BMS Medical Monitor/designee, there are no sequelae that would place the subject at a higher risk when receiving BMS-986165
- The above must be discussed with the BMS Medical Monitor prior to rescreening or recommencing IP (as applicable).

10 STATISTICAL CONSIDERATIONS

10.1 Sample Size Determination

Approximately 50 subjects will be randomized in a 3:1 ratio to BMS-986165 12 mg BID or placebo BID, respectively (ie, approximately 37 subjects receiving BMS-986165 12 mg BID and approximately 13 subjects receiving placebo BID). Subjects randomized to BMS-986165 6 mg BID under the Original Protocol or Protocol Amendment 01 will continue receiving BMS-986165 6 mg BID in the double-blind treatment period. Approximately 3 subjects are expected to be randomized to the BMS-986165 6 mg BID dose arm.

10.1.1 Clinical Response Rate

The assumed rate of clinical response at Week 12 is based on the observed rates of clinical response in recent clinical trials of mirikizumab (an anti-IL-23p19 antibody; Week 12 endpoint, NCT02589665)³¹ and ustekinumab (an anti-IL-12p40 antibody; Week 8 endpoint, NCT02407236).¹

Assuming BMS-986165 12 mg BID will provide a similar clinical response rate as was observed in these UC trials, the expected clinical response rate is assumed to be approximately 60%. If the observed clinical response rate in this study is the same as the assumed rate reported above, the estimated 95% CI of clinical response rate is expected to be (42%, 75%) for the BMS-986165 12 mg BID arm at Week 12 using the Clopper-Pearson exact method.

With the sample size selected for this study, the expected 95% CI of clinical response rate for the BMS-986165 12 mg BID arm will exclude a placebo rate of 33% (95% CI: 29%, 37%) reported in a recent meta-analysis of clinical trials in UC.⁵⁶

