3.1.5 BMS-986165 and Inflammatory Bowel Disease Studies: Overview

Study IM011024 is a multicenter, randomized, double-blind, placebo-controlled, parallel group, Phase 2 clinical trial designed to evaluate the safety and efficacy of BMS-986165 6 mg BID PO, compared with placebo, in subjects with moderate to severe UC. The primary endpoint is at Week 12. Following a 12-week induction period, eligible subjects enter a 40-week maintenance period. An additional 52-week open-label extension (OLE) period (to Week 104) is available for subjects who continue to derive clinical benefit. Topline results from Study IM011024 indicate that BMS-986165 6 mg BID compared to placebo BID did not meet primary efficacy endpoint of clinical remission at Week 12 or the predefined secondary efficacy endpoints. The safety profile of BMS-986165 was consistent with previously reported studies in psoriasis and psoriatic arthritis, and no new safety signals were observed. The study remains ongoing, and results from the Week 52 and Week 104 endpoints are not yet available.

Study IM011023 is a multicenter, randomized, double-blind, placebo-controlled, parallel group, Phase 2 clinical trial designed to evaluate the safety and efficacy of BMS-986165 6 mg BID PO and 3 mg BID PO, compared with placebo, in subjects with moderate to severe CD, following a 12-week induction period. After the induction period, eligible subjects enter a 40-week maintenance period. An additional 52-week OLE period (to Week 104) is available for subjects who continue to derive clinical benefit.

Study IM011077 is an open-label, long-term extension study to evaluate the long-term safety and efficacy of BMS-986165 6 mg BID in subjects who have previously been enrolled in a Phase 2 BMS-986165 study for moderate to severe CD (Study IM011023) or moderate to severe UC (Studies IM011024 and IM011127).

Study IM011127 (the current study) is a multicenter, randomized, double-blind, placebo-controlled, parallel group, Phase 2 clinical trial designed to assess the safety and tolerability, efficacy, and biomarker response of BMS-986165 12 mg BID PO following a 12-week treatment period. An additional 40-week OLE period (to Week 52) is available for eligible subjects.

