10.4.1.1 Primary Endpoint

Analysis Method:

The proportion of subjects achieving clinical response at Week 12 and the associated 95% CI for the BMS-986165 12 mg BID treatment arm will be estimated using the Clopper-Pearson exact method. Supportive analysis using logistic regression for the clinical response (binary endpoint) may be performed, and the odds ratio between treatment groups and the corresponding 95% CI may be provided if the data are sufficient to do so.

Imputation Method:

Occurrence of intercurrent events may have an impact on the estimand of interest for the following types of subjects: (1) subjects who discontinue treatment or study early (ie, prior to Week 12); (2) subjects who start a protocol prohibited medication/therapy; or (3) subjects who are lost to follow-up or have otherwise missing endpoint data at or prior to the Week 12 assessment. In these cases, the primary endpoint will be determined using the “Composite Strategy” as defined in the International Council for Harmonisation (ICH) E9 (R1) addendum and will be considered a measure of nonresponse to treatment.⁵⁸ Subjects with the identified intercurrent event(s) will have their clinical response endpoint imputed as being a “nonresponder.” This is commonly known as nonresponder imputation.

Sensitivity analyses using different imputation methods may be performed and will be defined in the SAP.

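### Does section 10.1.1 promise that the 12 mg confidence interval will exclude a 33% placebo rate, when this is only probable?

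*Combined protocol and SAP*

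**What the plan says.** Section 10.1 gives the size of the study: "Approximately 50 subjects will be randomized in a 3:1 ratio to BMS-986165 12 mg BID or placebo BID, respectively", with "approximately 37 subjects receiving BMS-986165 12 mg BID".

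Section 10.1.1 takes its planning value from trials of two antibodies: "the expected clinical response rate is assumed to be approximately 60" percent. It then sets a condition, "If the observed clinical response rate in this study is the same as the assumed rate reported above", and under that condition gives a 95% Clopper-Pearson interval of 42% to 75% for the 12 mg arm.

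The last paragraph of 10.1.1 has this expected interval as its subject. It says that, with the chosen sample size, the expected interval for the "BMS-986165 12 mg BID arm will exclude a placebo rate of 33% (95% CI: 29%, 37%) reported in a recent meta-analysis".

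The Synopsis (Statistical Methods) says that the sample size does not rest on power for comparisons among treatment groups, and that it was selected for adequate precision of estimation in the 12 mg arm. Under section 10.4.1.1 the Week 12 response proportion and its 95% interval "will be estimated using the Clopper-Pearson exact method". A supportive logistic regression may be added.

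**The concern.** The word *will*, coming straight after a reference to the chosen sample size, can be read as a guaranteed property of the design: run the trial with 37 subjects and the interval clears the historical placebo rate. No such guarantee exists, because the observed count varies even if the true rate is exactly 60%.

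The single planning value adds to the unease. It comes from other drugs, while section 3.1.5 reports that this molecule at 6 mg BID "did not meet primary efficacy endpoint of clinical remission at Week 12 or the predefined secondary efficacy endpoints" in ulcerative colitis. If the true rate at 12 mg were well below 60%, exclusion of 33% would become uncertain.

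At stake would be the efficacy case for 37 subjects, and a later reading of an interval that includes 33% against a promise that the design could not keep.

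**Working it through.** **Inputs.** n = 37 (section 10.1); planning rate 60%, stated interval 42% to 75%, benchmark 33% with limits 29% and 37% (section 10.1.1); two-sided 95% Clopper-Pearson interval (sections 10.1.1 and 10.4.1.1). The Full Analysis Set holds all randomized subjects (section 10.2), and missing outcomes count as nonresponse (section 10.4.1.1), so dropout does not shrink the denominator.

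**Step 1: reproduce the plan's interval.** 0.60 × 37 = 22.2, so the nearest count is 22 (22/37 = 59.5%). For x responders of n, the lower limit is the 0.025 quantile of Beta(x, n − x + 1) and the upper limit is the 0.975 quantile of Beta(x + 1, n − x).

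- Lower limit, Beta(22, 16): 0.4210
- Upper limit, Beta(23, 15): 0.7525

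In whole percent this is 42% to 75%, as stated.

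**Step 2: check the sentence as written.** 42.1% is above 33% and above 37%. The sample size is approximate, so the neighbouring values matter too: 22/36 gives 43.5% to 76.9%, and 23/38 gives 43.4% to 76.0%. The expected interval excludes 33% in each case.

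**Step 3: check the stronger reading.** Lower limits for n = 37:

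| Responders | Lower limit |
|---|---|
| 18 | 31.9% |
| 19 | 34.4% |
| 20 | 36.9% |
| 21 | 39.5% |

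An interval above 33% therefore needs at least 19 responders, and one above 37% at least 21. The exact binomial tails for n = 37 are:

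| True rate | P(X ≥ 19) | P(X ≥ 21) |
|---|---|---|
| 60% | 0.892 | 0.718 |
| 55% | 0.730 | 0.482 |
| 50% | 0.500 | 0.256 |
| 45% | 0.270 | 0.102 |

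Only the 60% row uses a rate from the documents. The other three rates are assumptions made to show a range. At 60%, P(interval above 33%) is 0.854 for n = 36 and 0.922 for n = 38.

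**Step 4: compare the two readings with the text.** Step 3 would contradict the plan only if the plan claimed exclusion whatever the observed count. The two paragraphs of 10.1.1 belong together: the first defines the expected interval through its condition on the observed rate, and the second compares that interval with 33%. The plan gives no probability of exclusion, so no stated probability can be wrong.

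**The case for a change.** The best case for the concern accepts that the sentence is arithmetically true and says that it is incomplete.

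- **A benchmark goes beyond precision.** A pure precision argument needs only the width of the interval. Once 33% is brought in, the chance of clearing it is a natural design quantity. Section 10.1.2 does report probabilities for adverse events, at two assumed incidences: 1 − 0.90^37 = 0.98 and 1 − 0.94^37 = 0.90. Section 10.1.1 shows one outcome at one rate. This contrast is real. It shows that a further figure could have been given; it does not show that a given figure is wrong.
- **The benchmark carries weight.** The primary analysis is a single-arm interval, and 33% is the only external rate offered beside it. Yet section 10.4.1.1 contains no success criterion or decision rule that uses 33%. The trial also has a concurrent placebo arm, and section 3.1.5 already allows comparison with Study IM011024.
- **60% may be optimistic.** The missed endpoints in section 3.1.5 concern half the dose, a primary endpoint of clinical remission where this trial uses clinical response, and a comparison with placebo. The section gives no response rate and does not name the secondary endpoints. It gives reason for caution but does not yield a rate of 50% or 45% at 12 mg. The rationale for 12 mg is blacked out in the public text, so how the sponsor weighed the 6 mg result cannot be judged. Using the IM011024 placebo rate as the benchmark would be a preference, and the documents do not report that rate.
- **37% is a harder test.** It is, but the plan's comparison value is 33%, and the expected interval clears 37% as well.

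What stands is that a hasty reader could take *will* as a guarantee, and that no probability of exclusion is reported.

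**Conclusion.** The concern does not hold. The sentence in section 10.1.1 describes the interval expected if about 60% respond. That interval reproduces at 22/37 and lies above both 33% and 37%, by 42.1 − 33 = 9.1 and 42.1 − 37 = 5.1 percentage points. The probabilities of 89% at a true rate of 60% and 50% at a true rate of 50% are correct, but they answer a question that the plan does not claim to answer. For a sample size justified by precision, an 89% chance at the planning value does not show 37 subjects to be too few.

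This rests on reading the two paragraphs of 10.1.1 together, on the Synopsis statement that the size is not based on power for group comparisons, and on the absence of any rule tied to 33% in section 10.4.1.1. Adding a probability or softening one verb would be a matter of style; neither would alter the number of subjects, the analysis or the conclusion.
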